4.2 Exclusion Criteria

- 4.2.1 Unable to take capsules orally.
- 4.2.2 Requiring systemic non-*C. difficile* antibiotic therapy within 14 days prior to FMT.
- 4.2.3 Unwilling to stop taking non-dietary probiotics 24-96 hours prior to FMT.
- 4.2.4 Unable to stop taking bile acid sequestrants (e.g. cholestyramine) 24-96 hours prior to FMT.
- 4.2.5 Unable to stop use of drugs with CDI activity: oral vancomycin, oral or IV metronidazole, fidaxomicin, rifaximin or nitazoxanide 24-96 hours prior to FMT and after FMT.

4.2.6 Receipt of CDI monoclonal antibodies as treatment for the most recent bout of CDI.

4.2.7 Life expectancy of < 6 months.

4.2.8 In the opinion of investigator, subject for any reason should be excluded from the study.

4.3 Vulnerable Population in Research:

The elderly population particularly is susceptible to recurrent *C. difficile* infection (CDI) and some elderly patients may be cognitively impaired. Informed consent can be obtained from legally authorized representatives (LAR) if potential subjects have condition or circumstances that could impact their ability to make decision or consent. These subjects may include but are not limited to the cognitively impaired, demented, incapacitated, or otherwise mentally or physically incapable of communication. Before their enrollment, the study coordinators must be certain that a caretaker can properly record data called for in the study.

The investigators or designee will assess subjects on their abilities to understand information and express a reasoned choice concerning the nature of the research, consequences of participations for the subject's own situation, and consequences of the alternatives to participation. The investigators or designee will ask questions about the main elements of the study and judge whether the potential participant has a clear understanding.

When an LAR agrees to the participation of the subject in the study, the consent would be obtained either from the patient's legal guardian with the authority to make decisions regarding medical treatment (with proper paperwork to establish this) or a person designated as a surrogate decision-maker by the patient in a medical power of attorney or Advance Directive. The investigator or designee will ask for a copy of the legal document from the authorized representative. The LAR and the person obtaining consent would personally sign and date the consent form. A copy of the signed consent document will be given to the LAR.

4.4 Subject Pre-screening, Screening and Re-screening:

Patients will be referred by a physician or self-referral to the study. Patient/LAR or physician will be provided a pre-screening form and requested to return the form with signed medical release and *C. difficile* related medical record (via email/fax/mail) for eligibility review. Pre-screening form and medical record received electronically will be kept securely in an access controlled network file service and will not be shared with anyone outside the study team. Any paper record will be kept securely in locked cabinet with access control. For potential subjects who are pre-screened but do not enroll subsequently, the identifying information may be kept for 180 days of release, after which all identifying information will be destroyed and not retained with study records. A non-

identifiable information log will be maintained to assess the number of patients pre-screened and the reasons for exclusion or not participating in the study.

If a potential subject seems eligible on pre-screening, an appointment will be set up for in person enrollment and screening. Study personnel will advise potential subject as to this study's purpose, requirements, and anticipated risks. Subject will be given the chance to review the informed consent form, will have the study explained in detail and any questions answered. Subjects who choose to enroll will sign the informed consent form, and the date of the consent form will serve as the first day of enrollment into the study. Subjects will be provided with a copy of the signed consent form.

Consented subjects who meet all inclusion and none of the exclusion criteria will be assigned a Subject ID (FMT-R-03-XXX) and randomized. Subjects who do not meet the inclusion criteria and/or meet exclusion criteria will be considered screen failures. Screen failures or subjects who exit the study before receiving Treatment Day 1 dose will not count towards total randomization and their assigned Subject IDs will be retired. Screen failures or subjects who exit the study before receiving treatment Day 1 dose are allowed to be re-screened once for eligibility. Re-screens will be re-consented and re-randomized to a new Subject ID to ensure maintenance of blinding.

Subject's attending physician will continue to treat the subject's primary disease(s) while the subject is a part of the study. The subject will continue all medications deemed as necessary and they will be recorded in the subject's study record. Physicians caring for these subjects will have no limitations in how the subject's primary disease(s) are managed. Antibiotics for *C. difficile*, non-dietary probiotics, and bile-acid sequestrants must be stopped 24-96 hours before the treatment. All other antibiotics must be stopped 14 days prior to treatment. Subjects will be recommended not to use non-dietary probiotics and bile-acid sequestrants within 60 days after FMT treatment; however, subjects who take probiotics and bile-acid sequestrants within 60 days after treatment will not be excluded.

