INCLUSION CRITERIA	All subjects 1. Male and female subjects 18 years of age or older. 2. Sexually active male and female subjects of childbearing potential agree to use an effective method of birth control during the study. 3. Female subjects of childbearing potential must have a negative pregnancy test on the day of the procedure prior to administration of study drug. 4. Subject/LAR willing and able to provide informed consent. 5. Able to follow study procedures and follow-ups. 6. Subject must have an attending physician who will provide non-transplant care. 7. Medical history of ≥ 3 bouts of CDI in outpatient or ≥ 2 bouts of CDI in inpatient with either group having ≥ 2 positive fecal tests for C. difficile toxin and at least one bout of CDI within 6 months of enrollment. 8. Received at least two courses of standard-of-care antibiotic therapy for CDI. 9. Have a refrigerator at home to store the second dose of FMT overnight.

EXCLUSION CRITERIA	
 1. Unable to take capsules orally. 2. Requiring systemic non-C. difficile antibiotic therapy within 14 days prior to FMT. 3. Unwilling to stop taking non-dietary probiotics 24-96 hours prior to FMT. 4. Unable to stop taking bile acid sequestrants (e.g. cholestyramine) 24-96 hours prior to FMT. 5. Unable to stop use of drugs with CDI activity: oral vancomycin, oral or IV metronidazole, fidaxomicin, rifaximin or nitazoxanide 24-96 hours prior to FMT and after FMT. 6. Receipt of CDI monoclonal antibodies as treatment for the most recent bout of CDI. 7. Life expectancy of < 6 months. 8. In the opinion of investigator, subject for any reason, should be excluded from the study.
DURATION OF FOLLOWUP	The duration of study participation for each subject is up to 216 days including screening (14 days), treatment (2 days) and follow-up (180-200 days).
STUDY POPULATION	The target population are adults (≥ 18 years old) with ≥ 3 bouts of CDI in outpatients or ≥ 2 bouts of CDI in an inpatient with either group having ≥ 2 positive fecal tests for C. difficile toxin and at least one bout of CDI within 6 months of enrollment.
STUDY BLINDING	This is a double-blinded study for the groups randomized to receive pre-treatment bowel prep and Imodium.

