5.3 Method of Assigning Subjects to Study and Treatment

The four groups will be assigned randomly on 1:1:1:1 ratio by computer table randomization method at the University of Texas School of Public Health. After enrollment of subject in the study, the study coordinator will send an email to the authorized person for randomization at the University of Texas School of Public Health including the schedule (date and time) of study procedure. The study coordinator will receive an email from the authorized person providing the subject identification number and confirmation of date and time for study drug delivery. For subjects randomized to unblinded treatment group 4, it will be noted in the email not to use bowel prep and Imodium.

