- Enrollment visit will occur on day -14 to -1 during which the informed consent will be obtained; inclusion and exclusion criteria will be reviewed; demographics, current medications, the medical history, and the CDI history (including information on solicited symptoms for two-week period prior to enrollment) will be reviewed and recorded. Subjects may already be taking or just have been prescribed antibiotics per standard of care to control recurrent CDI symptoms at the time of enrollment. Subjects who have completed antibiotic therapy will receive four days of oral vancomycin or fidaxomicin daily (PI can call in prescription if needed) prior to the 24-96 hours washout period. A stool collection kit along with IRB approved pretreatment prep instructions, pre-treatment diary, stool collection instructions and directions to drop specimen will be provided to subject.
- A stool sample will be collected by subject during enrollment period (prior to bowel prep) and a pre-treatment diary card will be completed by subject. Study personnel can obtain the stool and diary from subject on treatment Day 1 clinic visit. This stool will go to EPDL at the University of Texas School of Public Health.
- Day -4 to -1 before treatment: remind the subject by email or phone call about clinic appointment time, stopping antibiotic/probiotic/ bile-acid sequestrant, pre-treatment preparation and bringing pre-treatment diary and stool. Day -4 to -1(96 to 24 hours) before treatment: the last day of *C. difficile* antibiotics, non-dietary probiotics and bile-acid sequestrants. Subjects continue taking routine prescription medications.
- Day -1 before treatment: subjects follow a clear liquid diet the entire day. In the evening around 6:00pm, subjects (treatment groups 1-3) who were instructed by the study team during the enrollment will ingest bowel prep.

Treatment Visit: Day 1 (Clinic Visit)

- Subjects are recommended to continue clear liquid diet until after treatment for 1 hour.
- Ensure subject in treatment groups 1-3 has taken bowel prep the evening before and 4mg (2 capsules) of loperamide (Imodium) the morning of treatment (If Imodium

is missed, can be taken within 12 hours of FMT treatment). If bowel prep is missed, subject can proceed with FMT and will be recorded as protocol deviation.

- Collect and review the pretreatment diary with subject to determine baseline pattern of solicited symptoms to assess for adverse events.

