10.2.3 Analysis Populations

Two primary analyses will be performed:

- 1) Analysis for safety and efficacy between three groups (1-3) receiving varied doses of lyophilized product generated from stool (50g for both treatment days; 100g on the first treatment day and 50g on the second treatment; 100g for both treatment days)
- 2) Analysis for safety and efficacy between two groups (3 and 4) with and without bowel preparation and Imodium receiving same high doses of lyophilized product (100g for both treatment days).

- All analyses will be conducted using the intent-to-treat population. Intent-to-treat is defined as all subjects who have started the procedure.
- Listings and summary tables with descriptive statistics will be prepared for demographic data (gender, date of birth, race/ethnicity), and medical history data.

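### Subjects who leave between randomization and the Day 1 dose go uncounted and may be re-randomized once, with group 4 status already known, so the primary group 3 vs 4 comparison is open to selection and the intent-to-treat set is really a modified one

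*Combined protocol and SAP*

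**What the plan says.** **Timing.** Section 4.4 assigns an ID and randomizes consented, eligible subjects. Table 1 places randomization in the enrollment column, Day -14 to -1.

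**Disclosure before dosing.** The coordinator learns group 4 status from the randomization email (5.3): "For subjects randomized to unblinded treatment group 4, it will be noted in the email not to use bowel prep and Imodium". Subjects learn it from whether they are told to take prep (7.2): "subjects (treatment groups 1-3) who were instructed by the study team during the enrollment will ingest bowel prep". Section 8.2 repeats the prep instruction to groups 1-3 in the Day -4 to -1 reminder. The Synopsis limits the blind accordingly: "This is a double-blinded study for the groups randomized to receive pre-treatment bowel prep and Imodium".

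**Pre-dose exits.** Section 4.4 says: "Screen failures or subjects who exit the study before receiving Treatment Day 1 dose will not count towards total randomization". Their IDs are retired, one re-screen is allowed, and re-entry means a new draw: "Re-screens will be re-consented and re-randomized to a new Subject ID to ensure maintenance of blinding".

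**Analysis set.** Section 10.2.3 makes group 3 vs group 4 one of two primary analyses and puts all analyses on an intent-to-treat population: "Intent-to-treat is defined as all subjects who have started the procedure". It does not say which event counts as starting.

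**The concern.** An intention-to-treat comparison is protected because nobody can leave the set for a reason linked to a known assignment. Here the set closes at the start of the procedure, after the assignment has been partly revealed. Someone who learns that prep is required, or that it is not, can leave, disappear from the count, and return with a fresh chance of the other condition. Staff also have a route: section 4.2.8 lets the investigator exclude a subject for any reason, section 4.5 lets the investigator withdraw one for any reason, and some eligibility checks fall on Day 1.

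Group 3 vs 4 asks what prep and Imodium do. Prep falls between randomization and the dose, so a subject who leaves because of it drops out of the comparison meant to evaluate it. If leavers differ in prognosis from those who stay, the observed difference mixes the effect of prep with the effect of who remained.

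**Working it through.** **1. Where the exposure lies.** Selection by assignment needs three things: knowledge of the assignment, a way out, and a set that closes afterwards.

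- *Group 3 vs 4:* all three are present (5.3 and 7.2; 4.4; 10.2.3).
- *Groups 1-3 against each other:* the first is missing. Placebo capsules equalize the capsule count and containers are opaque (5.1, 5.2), so a pre-dose exit cannot follow dose while the mask holds.

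**2. Whether blinding requires a new draw.** Group 4 has no blind to maintain. For groups 1-3, a new ID is enough: the randomization office at the School of Public Health issues the IDs (5.3) and could link a new ID to the first assignment without telling the clinic.

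**3. What starting means.** If it means the Day 1 dose, all groups enter the set at the same point. If it includes prep, groups 1-3 enter on Day -1 and group 4 on Day 1. The text allows either reading.

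**4. Size, as illustration only.** The plan gives no pre-dose exit rate. The 10% in section 10.2.2 is overall loss to follow-up, split neither by stage nor by group. The benchmark is the planned group 3 vs 4 difference, 88% - 80% = 8 points. Its standard error at 90 per group is √[(0.88×0.12 + 0.80×0.20)/90] = 5.4 points.

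*Illustration A: exit from one group, no return.* Assume true success of 80% in both groups, a fraction f of one group leaving, and success s among leavers. Success among those dosed is (0.80 - f·s)/(1 - f). For f = 0.10 and s = 0.50, this is (0.80 - 0.05)/0.90 = 83.3%, a spurious 3.3 points. The last column is the two-sided 5% pooled z test at 90 per group.

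| f (assumed) | s = 0.70 | s = 0.50 | False-positive rate |
|---|---|---|---|
| 5% | 0.5 points | 1.6 points | 5.1% to 5.8% |
| 10% | 1.1 points | 3.3 points | 5.4% to 8.9% |
| 20% | 2.5 points | 7.5 points | 7.1% to 27.5% |

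The group that loses the poorer-prognosis subjects looks better. The sign reverses if the other group loses them, or if better-prognosis subjects leave.

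*Illustration B: exit and one re-draw.* Assume 30% of subjects are frail, with success 18 to 30 points lower. A fraction e of the frail subjects assigned to prep leave, all return, none leaves again, and nobody else exits. Of all frail subjects, 0.75e are re-drawn, and each group receives a quarter of them (0.1875e). Group 4 then holds 0.25 + 0.1875e of the frail, and group 3 holds 0.25 - 0.25e + 0.1875e = 0.25 - 0.0625e. Each group keeps a quarter of the non-frail (0.70 × 0.25 = 0.175 of all subjects).

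For e = 0.5:

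- group 4 frail share = 0.3×0.34375/(0.3×0.34375 + 0.175) = 37.1%
- group 3 frail share = 0.3×0.21875/(0.3×0.21875 + 0.175) = 27.3%
- shift = 9.8 points × 0.18 to 0.30 = 1.8 to 2.9 points

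For e = 0.1 the shares are 31.5% and 29.5%, a shift of 0.4 to 0.6 points. For e = 0.3 they are 34.4% and 28.4%, a shift of 1.1 to 1.8 points. Re-drawn subjects make up 0.3×0.75×e of the total, about 2% to 11%.

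**The case against.** **Prep refusal need not lead to exit.** A reader might infer that subjects who will not or cannot take prep must leave groups 1-3. The documents do not support this. Sections 7.2, 8.1 and 8.3.1 and a Table 1 footnote let a subject who missed prep proceed, with a protocol deviation recorded. Imodium may be taken up to 12 hours after treatment, and a different prep is provided for impaired kidney function. This stands: it limits prep-driven exits, though it does not prevent someone leaving on being told of prep.

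**The exclusions are not concealed.** A reader might say that the ITT label hides them. Section 10.2.3 prints its definition, section 4.4 states how exits are handled, and section 4.6 records the reason for withdrawal. The label is wrong, but it is not covert. What is missing is a planned table of exits by group.

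**A fresh draw has some merit.** It restores concealment at re-entry. If the first assignment is kept, subject and staff may know prep status at re-consent. That is a genuine trade-off. It is the smaller problem if everyone randomized is analysed by first assignment, because then neither leaving nor returning changes the group.

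**The effect may be small.** At low exit rates the shifts are well under the 5.4-point standard error. The comparison has only about 31% power at 90 per group for 88% vs 80%, and section 10.2.6 expects trends only. This argues against a higher rating. It does not remove the problem, because a trend is as open to selection as a significant result.

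**Conclusion.** The point holds as a design and labelling defect confined to comparisons that involve group 4, chiefly the primary group 3 vs 4 analysis. Followed as written, the plan lets pre-dose exit and one re-draw depend on known prep status, and its intent-to-treat set is modified ITT.

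Three stronger readings are not supported:

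- **That the comparison will be biased, or biased in a known direction.** No exit rates or reasons are given, so this is a risk of unknown size and sign. The shifts of 0.4 to 7.5 points rest wholly on the assumptions listed with them.
- **That leavers are formally replaced.** This can be inferred from section 4.4 together with the target of 360 evaluable subjects in section 10.2.4, but no replacement rule is written.
- **That the whole trial is compromised.** The dose comparison among groups 1-3 is largely protected by masking, and re-screening is limited to once.

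The change should be made. It is cheap, and first assignments and exit reasons that are not kept during the trial may not be recoverable at analysis.

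**What to change.** 1. **Section 4.4.** State that a subject re-screened after randomization keeps the first assigned group, with any new ID linked to it by the randomization office, and stays in the count of randomized subjects.
2. **Section 10.2.3.** Define ITT as all randomized subjects by first assignment. Rename the present set modified ITT, and define starting as receipt of the Day 1 dose in all four groups.
3. **Reporting.** Tabulate pre-dose exits by assigned group with reasons. Separate ineligibility found after randomization (for example a positive Day 1 pregnancy test) from voluntary or investigator withdrawal.
4. **Sensitivity analysis.** Analyse group 3 vs 4 in all randomized subjects, with a stated rule for the never-dosed. The rule is essential because withdrawn subjects stop all study procedures (4.6) and the endpoint is counted from FMT. One option is to count the never-dosed as failures in both groups, with best-case and worst-case bounds alongside.

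The bounds matter because counting leavers as failures is not neutral. In Illustration A with f = 0.05 and s = 0.60, the dosed-only figure is (0.80 - 0.03)/0.95 = 81.1%, a shift of +1.1 points. Counting leavers as failures gives 0.80 - 0.03 = 77%, a shift of -3.0 points. The bounds on the difference span the sum of the two exit fractions, so 5% in each group gives a 10-point span.

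**Cost.** A few sentences, some extra IDs to track, one table and one sensitivity analysis. Subjects who re-enter may know their prep status when they re-consent. If 360 dosed subjects are still wanted, assumed pre-dose exits of 2%, 5% or 10% mean randomizing 360/(1 - rate) = 368, 379 or 400.

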4.5 Subject Withdrawal or Termination

Subject's participation is considered complete approximately 180-200 days after FMT procedure; however, subjects may withdraw from the study at any time for any reason, without any consequence. In addition, a subject may be withdrawn from the study by the investigator for any reasons including the following:

1. Lost to follow-up
2. Adverse Event (AE) or Serious Adverse Event (SAE)

3. Protocol violation/non-compliance
4. Subject decision to withdraw consent
5. Investigator decision to terminate the study

4.6 Handling of Withdrawals and Discontinuation of Treatment

Subjects are free to withdraw at any time. The primary reason for withdrawals from the study will be recorded in the study exit form. Subjects who withdraw or are withdrawn will be encouraged to complete an Early Termination Phone Visit to assess for AEs. Subjects who withdraw will be discontinued from all study procedures.

4.7 Lost to Follow-up

If subjects miss a treatment or follow-up, three attempts will be made by telephone or e-mail to contact and locate subjects. The contact attempts will be recorded on the study exit form.

4.8 Receipt of Systemic Antibiotics, Non-Dietary Probiotics and Bile-acid Sequestrants during the Trial

If a subject takes a systemic (non-topical) antibiotic within 60 days after FMT treatment, they will be excluded from the efficacy part of the study and only followed for safety. Exclusion from efficacy means subjects will no longer provide stool specimens. However, subjects will continue to have phone visits and submit diaries till 180-200 days (the end of the study) for safety assessment (AEs). If they take systemic antibiotics more than 60 days after FMT treatment, they will be included in all aspects of the study.

Subjects will be recommended not to use non-dietary probiotics and bile-acid sequestrants within 60 days after FMT treatment; however, subjects who take probiotics and bile-acid sequestrants within 60 days after treatment will not be excluded and continue to be followed for efficacy and safety.

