6. TREATMENT FAILURES AND RETREATMENT

Treatment failure is defined as the presence of diarrhea (passage of ≥ 3 watery stools per 24-hour period for two consecutive days) and *C. difficile* toxin A/B positive stool within 60 days of FMT treatment and receipt of anti-*C. difficile* antibiotics.

If diarrhea (passage of ≥ 3 watery stools per 24-hour period for two consecutive days) occurs and CDI recurrence is suspected, subjects should inform study team and be recommended to contact their physician to perform a stool test for *C. difficile*. EPDL will test scheduled stool specimens and any unscheduled illness stool submitted up to days 60-70 after treatment for *C. difficile* toxins A/B in weekly batches but this should not delay treatment. If the test is positive, they should be treated by their physician. The Principal Investigator will be available for consultation with the attending physician. Subjects who are determined treatment failures by the investigator will not be followed further for clinical parameters. They will be offered FMT retreatment with maximum dose (200g) from a different donor product if the subject and their physician wish to pursue this treatment. After at least 10-20 days of anti-CDI antibiotics (vancomycin or fidaxomicin) subjects will be eligible for second FMT after 24-96 hour washout. If there is a delay between completing treatment and second FMT, the subject will receive at least four days of vancomycin or fidaxomicin prior to FMT (PI can call in prescription if needed) to complete the treatment 24-96 hours before second FMT. Subjects will be recommended to follow a clear liquid diet the entire day before retreatment clinic visit. Bowel preparation and Imodium will not be required before retreatment. During retreatment clinic visit, vital signs and weight will not be assessed and subjects will be observed for 30 minutes after dosing.

Retreatment Dosage: Day 1 (Clinic Visit)

- Subjects are recommended to continue clear liquid diet until 1 hour after retreatment.

- Perform urine pregnancy test on all female subjects of childbearing potential prior to FMT administration.
- Administer Day 1 dose and dispense Day 2 dose.
- Observe the subject for 30 minutes after dosing.
- Remind subject that Day 2 dose should be taken the next morning on empty stomach with water and release the subject.

Retreatment Dosage: Day 2 (Phone Visit)

- Ask that subject has taken the Day 2 dose.
- Ask for any adverse events since Day 1 assessment.

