7.3 Clinical Response Evaluation

The clinical evaluation will include an evaluation of CDI recurrence to assess clinical response on each follow-up contact for 60 days after FMT.

If subjects experience diarrhea (3 or more watery stools/day for two consecutive days) and suspect CDI recurrence, they should inform the study team and be recommended to contact their physician to perform a stool test for *C. difficile*. EPDL will test scheduled stool specimens and any unscheduled illness stool submitted up to days 60-70 after treatment for *C. difficile* toxins A/B in weekly batches but this should not delay treatment. If the test is positive, they should be treated by their physician. The Principal Investigator will be available for consultation with the attending physician. A form letter may be faxed or emailed to subject's physician about CDI recurrence.

Subjects requiring a systemic Non- *C. difficile* antibiotic within 60 days following FMT treatment will be excluded from the study for efficacy analysis, but will be followed for safety. Exclusion from efficacy means subjects will no longer provide stool specimens. However, subjects will continue to have phone visits and submit diaries till 180-200 days (the end of the study) for safety assessment (AEs). Subjects requiring a systemic Non- *C. difficile* antibiotic 60 days after FMT treatment will continue to be followed for efficacy and safety.

Subjects will be recommended not to use non-dietary probiotics and bile-acid sequestrants within 60 days after FMT treatment; however, subjects who take probiotics and bile-acid sequestrants within 60 days after treatment will not be excluded and continue

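### Sections 4.8 and 7.3 give different antibiotic triggers for the same efficacy exclusion, and 4.8 read literally would catch most treatment failures

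*Combined protocol and SAP*

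**What the plan says.** The efficacy exclusion for antibiotic use appears twice in the protocol, with different triggers.

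- Section 4.8: "If a subject takes a systemic (non-topical) antibiotic within 60 days after FMT treatment, they will be excluded from the efficacy part of the study". The only description of the drugs is that they are systemic, glossed as non-topical. There is no exception for C. difficile treatment.
- Section 7.3: "Subjects requiring a systemic Non- *C. difficile* antibiotic within 60 days following FMT treatment will be excluded from the study for efficacy analysis". Here only drugs not aimed at C. difficile trigger the rule.

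Both sections explain the consequence in the same way: "Exclusion from efficacy means subjects will no longer provide stool specimens". Both keep the subject on phone visits and diaries to day 180-200 for safety.

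The failure definition (Synopsis and section 6) has three parts: diarrhea, a toxin-positive stool, and C. difficile treatment. Section 6 words the last two as "positive stool within 60 days of FMT treatment and receipt of anti-*C. difficile* antibiotics". It also sets a separate path for failures: "Subjects who are determined treatment failures by the investigator will not be followed further for clinical parameters".

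Section 10.2.3 states: "All analyses will be conducted using the intent-to-treat population", meaning everyone who started the procedure. Section 10.2.6, on the efficacy analyses, does not mention antibiotic use.

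**The concern.** One exclusion has two triggers, and nothing says which governs. The difference matters because the drugs that 4.8 covers and 7.3 does not are the drugs a subject receives on failing. A cured subject has no recurrence to treat, so exclusion under 4.8 would depend on the outcome. Failures would leave, cures would stay, and the arms with more failures would lose more subjects. Cure rates would rise in every arm, most in the lowest-dose arm, and the dose contrast would shrink.

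There is also a problem of ascertainment. The study laboratory tests stools in weekly batches, and sections 6 and 7.3 say that this should not hold up treatment. A subject may therefore start a CDI drug on suspicion. Under 4.8 that ends stool collection, possibly before the toxin part of the failure definition has been settled. Under 7.3 collection continues.

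**Working it through.** **1. Do C. difficile drugs fall under 4.8?** Exclusion criterion 4.2.2 adds a non-C. difficile qualifier to systemic antibiotics where CDI drugs are to be left out. Section 4.4 likewise separates CDI antibiotics from all others. Criterion 4.2.5 lists the CDI drugs, including oral vancomycin and oral or IV metronidazole, which are not topical. On its wording, 4.8 includes them.

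**2. Does every failure trigger 4.8?** No. In the failure definition the 60-day window attaches to the diarrhea and the toxin-positive stool. Antibiotic receipt is added without a window. A late recurrence first treated after day 60 is a failure but escapes 4.8. The literal rule catches most failures, not all.

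**3. The plan's own power figure.** Section 10.2.2 assumes efficacy of 70% (Group 1), 80% (Group 2), 88% (Group 3) and 80% (Group 4), with 348 recipients (87 per group), two-sided alpha 0.05 and 85% power. For a four-group Pearson chi-square with 3 df:

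- mean rate = (0.70 + 0.80 + 0.88 + 0.80)/4 = 0.795
- sum of squared deviations = 0.009025 + 0.000025 + 0.007225 + 0.000025 = 0.0163
- noncentrality = 87 × 0.0163/(0.795 × 0.205) = 8.70
- power = 69.5% (simulation 69.6%)

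The stated 85% does not reproduce. That is a separate matter. Here the starting value is about 70%.

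**4. Expected failures at 87 per group.** 87 × 0.30 = 26.1; 87 × 0.20 = 17.4; 87 × 0.12 = 10.4; 87 × 0.20 = 17.4. The total is about 71 of 348.

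**5. Effect if a share f of failures is removed.** Apparent cure = p/[p + (1 − p)(1 − f)]. For f = 0.5, Group 1: 0.70/(0.70 + 0.15) = 0.824. Group 3: 0.88/(0.88 + 0.06) = 0.936. Power is from 200,000 simulated trials per row. The share f is an assumption; the full range is shown.

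| f | Group 1 | Groups 2 and 4 | Group 3 | Group 3 − Group 1 | Four-group power |
|---|---|---|---|---|---|
| 0 | 70% | 80% | 88% | 18 points | 69.6% |
| 0.25 | 75.7% | 84.2% | 90.7% | 15 points | 58.2% |
| 0.50 | 82.4% | 88.9% | 93.6% | 11 points | 42.5% |
| 0.75 | 90.3% | 94.1% | 96.7% | 6 points | 23.2% |
| 1 | 100% | 100% | 100% | 0 | no comparison possible |

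Section 10.2.3 names the three-dose comparison (Groups 1-3) as a primary analysis. It behaves in the same way: at 90 per group, power is about 77%, 67% and 51% for f = 0, 0.25 and 0.50.

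**The case against.** A reader might infer that 4.8 as written deletes the treatment failures from the efficacy data, so that every arm would report 100% cure. The documents do not support that as a statement of what the plan does.

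- Section 4.8 explains exclusion only as the end of stool collection and never mentions the efficacy analysis. Section 7.3 does mention it, and already carries the narrower trigger. This stands in part: 7.3 attaches the same explanation to an exclusion from analysis, so 4.8 remains ambiguous.
- Section 10.2.3 puts all analyses on everyone who started the procedure. If that governs, the choice of trigger does not alter the primary result. This stands. However, 10.2.3 also conflicts with 7.3's exclusion, so it cannot show which drugs were meant.
- Failures have their own path in section 6, with no further clinical follow-up and then optional retreatment and withdrawal. The long safety follow-up in 4.8 does not fit it, which suggests that 4.8 was not written with failures in mind. This stands as evidence of intent.
- Removing every failure would leave the endpoint nothing to measure, so it cannot have been intended. This stands. It makes 100% removal an upper bound that, given step 2, even the literal rule need not reach.
- No document supports any particular share removed, and 10.2.6 expects trends rather than significance. Both points stand. The power figures are illustrative, although the distortion of the cure rates would affect a trend as well.

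**Conclusion.** The inconsistency between 4.8 and 7.3 is real, and under the literal 4.8 the exclusion depends on the outcome. Section 7.3 is probably the intended rule. Bias in the primary analysis requires 4.8 to be applied over the intent-to-treat statement. Without that, what remains is lost stool ascertainment in subjects treated on suspicion, and the same distortion in any efficacy-evaluable set built from 4.8.

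The size depends on the unknown share removed and on the plan's assumed cure rates. The direction does not: removal raises the apparent cure rate in every arm and narrows the gap between Groups 1 and 3. That intent can be guessed makes the correction uncontroversial, but it does not give the coordinator or the analyst a rule.

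**What to change.** 1. Insert the non-C. difficile qualifier in 4.8 so that its trigger matches 7.3.
2. State in 4.8, 7.3 and 10.2.3 that receipt of an anti-C. difficile antibiotic does not remove a subject from the efficacy analysis, that subjects meeting the section 6 definition count as failures, and that scheduled stool collection continues until failure status is classified.
3. State how subjects treated for suspected CDI without a positive toxin test are counted. Section 6 does not treat a toxin-negative subject as a failure, so one treated empirically could count as a success while on CDI therapy. Add a sensitivity analysis counting these subjects as failures.
4. Reconcile the remaining exclusion for non-CDI antibiotics with the intent-to-treat rule in 10.2.3.
5. Reconcile the follow-up of failures in section 6 with the follow-up of excluded subjects in 4.8.

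The cost is a short text amendment and one extra analysis, with no additional patients.
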